8.3. Sample processing and sequencing

Blood samples will be processed after extraction using commercial kits for RNA extraction. Subsequently, the *library*, a procedure by which the transformation of the RNA sample into short cDNA chains for sequencing is known. For this procedure, the commercial TruSeq-RiboZero-GlobinFree kit (Illumina) will be used. Subsequent sequencing (without ribosomal RNA and globin) will be performed by an external sequencing service provider. A sequencing with a read depth of at least 100 million reads will be requested.

8.4. Bioinformatic and computational analysis of the transcriptomics sample

The bioinformatic analysis of the sequenced samples will be performed from the .fastq files containing the raw data. These files will be fed to an *pipeline* analysis. It comprises a successive series of bioinformatic procedures, including sample quality control, alignment with the human genome and count of *reads* per identified gene. The transcripts to be identified correspond to messenger RNAs, non-coding RNAs, circular RNAs, and RNAs corresponding to the blood microbiome. The expression quantification of the transcripts is then transformed using a series of proprietary routines, to then be transformed into an image (US patent 62/944,063 (pending)). This image represents both the expression of the transcripts as a function of their expression level and the genomic position as well as the RNA subtype. The set of images, which represent the set of gene expression in peripheral blood, is subsequently entered into a neural network to generate training that classifies the samples according to it. All these bioinformatic and artificial intelligence procedures are carried out using *free use programs* (“*open access software*”) under a routine created by the study researchers, mainly using python for coding, and pyTorch for training the neural network.

8.5. Analysis of cardiac CT

The presence of CAC and its extension will be evaluated using both ordinal variables (number of segments with CAC and number of affected vessels, and qualitatively: absence, mild, moderate, and severe; and the number of coronary segments with calcification) as continuous variables (Agatston units). The presence and extension of calcifications at the level of the aortic valve and the thoracic aorta (Agatston units) will also be evaluated independently. The extent of aortic calcification will be evaluated in sections that include from the bifurcation of the pulmonary artery as the upper limit to the diaphragm as the lower limit.

Quantitative analysis of SCC will be performed using dedicated software (HeartBeat-CS, Philips Healthcare, Best, The Netherlands). Finally, the volume and density of epicardial fat will be calculated by evaluating the volume of tissue with a density between -190 and -30 HU located in the area between the epicardium and the pericardium, the bifurcation of the pulmonary artery as the upper limit, and the diaphragm as lower limit.

Finally, the density of the hepatic parenchyma will be calculated through a region of interest >100 mm² at the level of the right and splenic lobes. From these measurements, the presence of hepatic steatosis will be defined from a quotient of less than 1.

At least 20% of the participants (randomly selected) will have a double reading of the main outcome of the study (presence or extent of CACs). This reading will be carried out by an expert external to the group of researchers of the study and blind to the first reading. In case of disagreement, consensus will be sought between the two experts. The aim of this process is to enhance the internal validity of the study.

The epicardial fat volume analysis will be performed by experts from the University of Palermo (Italy).

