5.1. In silico developments

In our laboratory, we have developed a methodology for transcriptome analysis based on extensive bioinformatic processing of a biological sample and its subsequent interpretation employing a *deep learning algorithm*. In this way, we can incorporate all the genes read in a sequence and perform a classification using a supervised method. This algorithm has proven robust and highly accurate in our preliminary tests. The development comprises a *pipeline* that takes the RNA-seq sample in its crudest state and analyses it entirely, including coding and non-coding RNAs, circular RNAs and the blood microbiome. The algorithm is trained with all the samples of a cohort, previously classified, and later, the algorithm is validated with 10 or 20% of the samples.

The analysis of the efficiency of the algorithm was performed with different RNA-seq databases available in digital repositories. First, we used the GTEx database, which has taken *postmortem* from dozens of people and performed sequencing of them. In total, 30 different tissues containing 11,866 sequences were analyzed. The analysis of our algorithm achieved a correct prediction in 99.1% of the cases (figure 1). The few errors correspond to potentially similar tissues (for example, breast with fatty tissue).

Subsequently, we analyzed the Genomic Data Commons (GDC) database, which has RNA sequencing of biopsies from different tumors. We analyzed 10,000 biopsies distributed in 34 tumors. Again, the predictive capacity of the algorithm was very high, reaching 97.5% (figure 2). These two analyses show that the algorithm has a great classification capacity between multiple samples.

We then performed a sensitivity analysis of the algorithm. To do this, we started with 100 random samples taken from brain tumors from the GDC database, 50 of them corresponding to GBM and 50 of them to GL. With them, new training was carried out in which we achieved a precision of 100%, which translates into an area under the curve (ROC) of 1. Successively, we removed samples at random, performing effective training with only 30 samples (15 of each group). Therefore, the algorithm has a very efficient behaviour with a low number of clinical cases. This reflects the fundamental differences in gene expression between the two groups of tumors.

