1. To classify transcriptomes according to the presence and extent of coronary calcification by noncontrast cardiac CT.
2. Train artificial intelligence algorithms with information from the transcriptome to recognize the presence and extent of calcification in coronary arteries.

-
3. To determine the degree of diagnostic accuracy of the method to detect the presence and extent of coronary calcification non-invasively.

Secondary objectives

1. To determine the degree of diagnostic accuracy of the method to detect the presence and extent of:
 - Aortic
 - calcification Aortic valve calcification
 - Hepatic steatosis
 - Volume of epicardial fat
 - Volume of high-density epicardial fat (upper quartile)
 - Enlargement of cardiac cavities To
2. To explore differences in transcriptomics of peripheral blood between patients who did and did not develop a CV event during follow-up.
3. To explore different electrocardiographic patterns according to the results of cardiac CT and peripheral blood transcriptomics.
4. Generate a polygenic risk score (PRS) from the transcriptome and/or exome sequencing and associate it with the transcriptome and coronary calcification.

7. Methods

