7.1. Study Design

This trial will be a prospective observational study. A convenience sample will be carried out to include 800 patients who attend the ENERI Medical Institute, La Sagrada Familia Clinic, to undergo a cardiac CT without contrast (coronary calcium score), either for a medical indication or volunteers to an assessment of cardiovascular risk. The study will have a baseline stage in which a clinical evaluation will be performed, blood samples will be drawn for transcriptome analysis and laboratory analysis. Then, a DNA sample

obtained by swabbing the buccal mucosa will be taken. Subsequently, a non-contrast gated cardiac CT will be performed to assess the presence and extent of coronary calcification and other results of interest. At the end of patient enrollment, biological samples will be sequenced for in silico evaluation of the results. Finally, a 5-year clinical (telephone) follow-up will be carried out to collect data on the incidence of fatal and non-fatal cardiovascular events.

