9.3. Calculation of the sample size

The calculation of the number of patients to demonstrate a positive effect for the use of peripheral blood transcriptomics for the diagnosis of the presence of severe coronary calcification is carried out based on previous experiences by the group of researchers. There is still no standardized methodology in the medical literature to perform the sample calculation of this type of analysis, since it is very recent and is in the exploration phase. Studies *silico* carried out by this group of researchers and the preliminary clinical studies carried out previously, it was observed that at least a sample of 800 patients is necessary for a robust training of the artificial intelligence algorithm that detects transcriptional differences between patients with or without a solid tumor. (for example, breast tumor). Therefore, 800 patients will be included based on the minimum number necessary to perform an adequate training of an artificial intelligence algorithm.

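### The second CAC readings go to a random 20% or more of participants with no link to the validation scans; assigning the same reads to the validation set first would give every validation label a consensus reading.

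*Combined protocol and SAP*

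**What the plan says.** The CT reading of coronary artery calcification (CAC) is the reference for the primary aim. Section 6 states it as: "To determine the degree of diagnostic accuracy of the method to detect the presence and extent of coronary calcification non-invasively".

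On the quality of that reference, section 8.5 says: "At least 20% of the participants (randomly selected) will have a double reading of the main outcome of the study". On the second reader: "This reading will be carried out by an expert external to the group of researchers of the study and blind to the first reading". And then: "In case of disagreement, consensus will be sought between the two experts". The stated purpose is to strengthen internal validity. No second reading is promised for the remaining scans.

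On validation, the only share is in section 5.1, in the description of the group's pipeline: "the algorithm is validated with 10 or 20% of the samples". The same sentence opens: "The algorithm is trained with all the samples of a cohort, previously classified".

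Section 9.4 lists sensitivity, specificity and AUC. It does not define a validation set, say which CT reading is the reference, or plan an agreement statistic. Section 7.1 gives the size: "A convenience sample will be carried out to include 800 patients".

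**The concern.** Double reading helps the accuracy estimate only where the corrected label is the one the algorithm is scored against. A random sample of the whole cohort spreads the second readings over training and validation scans in proportion to their numbers, so most fall on training scans. Most validation scans would then still be judged against one reader.

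If label errors are unrelated to the algorithm's output, they pull measured sensitivity and specificity down. The planned number of second readings is enough to cover a validation set of either size in section 5.1, so the lost benefit comes from where the reads are placed and not from how many there are.

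**Working it through.** **The plan's own figure.** The 800 cannot be reproduced. Section 9.3 gives no prevalence, accuracy or precision target; it says "800 patients will be included based on the minimum number necessary to perform an adequate training of an artificial intelligence algorithm". The check below needs only the counts.

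**Step 1: coverage of the validation set.** Inputs are N = 800 (7.1), a double-read share of at least 20% (8.5) and a validation share of 10 or 20% (5.1).

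- Double reads: 0.20 × 800 = 160, a minimum.
- Validation scans: 0.10 × 800 = 80, or 0.20 × 800 = 160.
- If the sets are drawn separately, the overlap is hypergeometric with mean (validation n) × 160/800.

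| Validation set | Expected double-read (95% range) | Expected single-read | Double reads outside the set |
|---|---|---|---|
| 80 | 16 (10 to 23) | 64 | 144 |
| 160 | 32 (23 to 41) | 128 | 128 |

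The chance that random selection covers the whole validation set is effectively zero. If the reads go to the validation set first, coverage is 80/80 with 80 reads left over, or 160/160 with none left.

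**Step 2: what label error would do.** All inputs here are assumptions, because the documents give no reader-error rate or CAC prevalence. True sensitivity (Se) and specificity (Sp) are 80%. Single-read label error e is 1, 2 or 4%, symmetric and independent of the algorithm. Consensus is free of error. Prevalence p is 40% or 20%.

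- Loss in sensitivity = (1 − PPVref) × (Se + Sp − 1), where 1 − PPVref = (1 − p)e / [p(1 − e) + (1 − p)e].
- Loss in specificity is the same expression with p and 1 − p exchanged.
- With a random 20% corrected, replace e by 0.8e.

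Example (p = 0.40, e = 0.04): 1 − PPVref = 0.024/(0.384 + 0.024) = 0.0588, and 0.0588 × 0.60 = 0.035. With 0.8e = 0.032: 0.0192/(0.3872 + 0.0192) = 0.0472, and 0.0472 × 0.60 = 0.028.

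| Loss in sensitivity, points | e = 1% | e = 2% | e = 4% |
|---|---|---|---|
| p = 40%, all single-read | 0.9 | 1.8 | 3.5 |
| p = 40%, random 20% corrected | 0.7 | 1.4 | 2.8 |
| p = 20%, all single-read | 2.3 | 4.5 | 8.6 |
| p = 20%, random 20% corrected | 1.9 | 3.7 | 7.0 |
| Every validation label by consensus | 0 | 0 | 0 |

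At 40% prevalence the specificity losses with single reads are 0.4, 0.8 and 1.6 points.

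**Step 3: comparison with sampling error.** For a sensitivity of 80%, the standard error is √(0.8 × 0.2 / number of positives).

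- 160 scans at 40% prevalence: 64 positives, SE 5.0 points, 95% half-width 9.8.
- 80 scans at 40%, or 160 at 20%: 32 positives, SE 7.1, half-width 13.9.

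Every loss in the table is inside the matching 95% half-width. The largest single-read loss (8.6) exceeds one standard error for 160 scans at 20% prevalence.

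**The case against.** The strongest objection is that the plan defines no validation set for this study. The 10 or 20% describes the group's pipeline, in a sentence that also has training use all samples, and neither 8.4 nor 9.4 repeats it. A reader might infer that the double-read and validation sets are known to be independent. The documents do not say so; they only fail to link them. The one-in-five coverage is therefore conditional on separate drawing.

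A reader might also infer that consensus serves only to overwrite labels and that the two readings will never be compared, or that exactly 640 scans stay single-read. Replacing the label is the natural reading of 8.5 but is not stated, a comparison is not ruled out, and 640 is a maximum because 20% is a floor.

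Nor is the mixture of single and consensus labels a separate bias. With random selection it is a partly corrected reference, closer to the truth than single reads alone. For the same reason, going back to the first reading as a uniform reference under cross-validation would discard the correction already obtained.

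The size is also open to challenge. Sections 8.2 and 8.5 specify one scanner and dedicated scoring software, so error in calling CAC present or absent may be small. Extent of calcification is not quantified here. Consensus cannot correct an error that both readers share.

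A random quality-control sample is a defensible design and suits estimation of cohort-wide agreement. That use survives the change if the validation set is itself drawn at random.

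What remains is the allocation: the planned reads are enough to cover the validation labels, and nothing in the plan directs them there.

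**Conclusion.** The point holds as a low-cost improvement and is not a flaw that invalidates the primary analysis. If the double-read and validation sets are drawn separately, about 80% of validation labels rest on one reader, although 160 reads could cover all of them under either split in 5.1.

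The coverage figures rest on the document's counts plus separate random drawing. The bias figures rest wholly on the assumed error rate, prevalence and accuracy, on errors independent of the algorithm, and on error-free consensus. In the base case the single-read loss of 0.9 to 3.5 points of sensitivity is below one standard error, but it runs in one direction under these assumptions. Confidence in its size is low. The documents do not support a claim that the accuracy results will be materially wrong.

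**What to change.** - **Section 9.4:** define a held-out validation set of at most 20%, drawn at random and kept out of training, and state that its reference is the consensus reading (the common reading where the two readers agree).
- **Section 8.5:** assign the planned double reads to that set first. Any reads left over, 80 under a 10% split, go to a random sample of the other scans.
- **Agreement:** report kappa for presence of CAC and the ICC for the Agatston score from the two readings before consensus. This would supply the reader-error information the plan lacks.

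No extra reading is needed. The held-out set must be fixed before reads are assigned, and the full benefit applies only to a held-out split of at most 20%; cross-validation over all 800 would not gain it. Fewer training labels would be corrected: none of 640 instead of an expected 128 under a 20% split, and 80 of 720 instead of 144 under a 10% split.

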8.6. Storage of biological samples

The remainder of the RNA samples and all of the DNA samples will be stored in a freezer at -20° C to be used in future research. The biological samples will be coded (see Confidentiality of the data) to maintain the anonymity of the participants and will be stored at FLENI Escobar Headquarters. The storage place has the necessary equipment to ensure their proper preservation. The temperature and other storage conditions will be permanently monitored as part of the quality assurance of the biological samples. It also has an emergency plan with trained personnel with defined responsibilities to attend to alarms and take actions to restore the system in the event of a failure. The freezer that

preserves the biological samples and the monitoring systems are connected to a permanent electrical source, with an emergency generator with enough autonomy to ensure its uninterrupted operation.

Since the stored samples will not be used in this study, specific consent will be requested for their storage and subsequent analysis..

8.7. Patient follow-up

Patients included in the study will be contacted annually by phone call to collect the following data:

- Vital status.
- Cardiovascular events: New episodes of hospitalization due to acute ischemic syndrome, cerebrovascular event, heart failure or revascularization.
- New diagnoses of relevant chronic diseases.

If they cannot be contacted, the "alternative means of contact" provided by the patient will be used, in order to know their vital status or obtain a new contact number.

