8.7.1. Events of interest in the study during follow-up

- Death from any cause
- Acute ischemic syndrome: Diagnosis of acute myocardial infarction or unstable angina.
- New diagnosis of heart failure with preserved or impaired ventricular function.
- Vascular revascularization: performance of myocardial revascularization surgery, coronary angioplasty or peripheral vascular angioplasty.
- Cerebrovascular event: Diagnosis of cerebrovascular accident ("stroke") or transient ischemic attack.
- Cancer: new diagnosis of any type of cancer

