8.7.2. Verification and adjudication of events during follow-up

When an event of interest is reported during study follow-up, the "phase of verification" that consists of obtaining data on: type of event, date, place where it was treated and its corresponding source document (death certificate, epicrisis, complementary study, evolution of clinical history, etc.) where the diagnosis of the event appears with a doctor's signature. The study event adjudication committee will be made up of three medical investigators ([name]). Each of the members will analyze the documentation sent for the case separately and will adjudicate the event. If there is no agreement, it will be awarded by majority.

9. Guarantee and quality control of the data

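### The annual call's cardiovascular item covers only hospitalisations, while the events of interest need no admission, so non-admitted TIA, unstable angina and day-case angioplasty are likely to be under-captured for exploratory objective 2

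*Combined protocol and SAP*

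**What the plan says.** Section 7.1 (Study Design) plans five years of telephone follow-up to gather "data on the incidence of fatal and non-fatal cardiovascular events". Secondary objective 2 (section 6) then explores transcriptomic differences between patients with and without a CV event.

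Section 8.7 sets out the contact: "Patients included in the study will be contacted annually by phone call to collect the following data". Three items follow:
- whether the patient is alive (vital status);
- a cardiovascular item, worded "Cardiovascular events: New episodes of hospitalization due to acute ischemic syndrome, cerebrovascular event, heart failure or revascularization";
- a chronic-disease item, worded "New diagnoses of relevant chronic diseases".

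Section 8.7.1 lists the events of interest:
- for mortality, "Death from any cause";
- for acute coronary events, the entry "Acute ischemic syndrome: Diagnosis of acute myocardial infarction or unstable angina";
- for heart failure, the entry "New diagnosis of heart failure with preserved or impaired ventricular function";
- myocardial revascularisation surgery, coronary angioplasty or peripheral angioplasty, counted when performed;
- a diagnosis of stroke or TIA;
- a new cancer.

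None of these carries an admission requirement.

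Section 8.7.2 starts verification "When an event of interest is reported during study follow-up". It then obtains the event type, date, place of treatment and a source document, which may be a death certificate. Three adjudicators decide. No rule is given for calling a death cardiovascular. Section 9.4 (Analysis plan) covers descriptive statistics and diagnostic performance and does not mention the comparison in objective 2.

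**The concern.** What is collected is narrower than what is to be counted. If a caller follows the 8.7 list as written, a patient who had a TIA without admission, or an angioplasty as a day case, can truthfully answer no to the cardiovascular item. Adjudication starts from a report, so it cannot recover an event that nobody elicited. Unless the patient volunteers it, that patient would be analysed as event-free.

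Separately, objective 2 does not say which entries of 8.7.1 make up a CV event, and 7.1 speaks of fatal cardiovascular events without saying how one is recognised. Two analysts could form different event groups from the same file.

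At stake is the one objective that uses the follow-up CV events. An outpatient event not asked about in its year would later depend on recall and on records that can still be retrieved.

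**Working it through.** **Text comparison.** Each 8.7.1 event is set against the 8.7 item that could elicit it.

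| Event of interest (8.7.1) | If admitted | If not admitted |
|---|---|---|
| Death, any cause | vital status | vital status |
| Infarction or unstable angina | cardiovascular item | no clear item |
| Stroke or TIA | cardiovascular item | no clear item |
| New heart failure | cardiovascular item | possibly the chronic-disease item |
| Coronary or peripheral revascularisation | cardiovascular item | no clear item |
| Cancer | possibly the chronic-disease item | possibly the chronic-disease item |

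The chronic-disease item has no admission condition, but the plan does not say which diseases are relevant. TIA, unstable angina and angioplasty are acute events or procedures, so that item does not clearly reach them. These are where under-capture is likely.

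**Size.** The plan has no figure to reproduce. It gives no event rate, effect size, alpha or power for objective 2, and section 9.3 bases the 800 patients on algorithm training. Apart from N = 800, every input below is an assumption.

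*Illustration A.* Assume 40 CV events, of which 30–50% are TIA, heart failure or angioplasty, and 20–40% of those are outpatient and missed.
- Fewest missed: 40 × 0.3 × 0.2 = 2.4. Most missed: 40 × 0.5 × 0.4 = 8. Heart failure is included here although the chronic-disease item may catch it, so the upper figure leans high.
- Power for one marker differing by 0.5 SD, two-sided 5%: Φ(0.5/SE − 1.96), with SE = √(1/e + 1/(800 − e)) and e the events captured.
- e = 40: SE = 0.1622, 0.5/SE = 3.082, power 87%.
- e = 38: SE = 0.1662, 0.5/SE = 3.008, power 85%.
- e = 32: SE = 0.1804, 0.5/SE = 2.771, power 79%.
- Contamination of the comparison group in the worst case: 8/768 = 1.0%, so 0.5 SD becomes 0.5 × (1 − 0.0104) = 0.495 SD and power goes from 79% to 78%. Nearly all the loss comes from having fewer events.

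*Illustration B.* Vary the assumed 5-year risk, with 10–30% of events not elicited and the comparison-group contamination included.

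| Assumed risk | True events | Captured | Power, full capture | Power, under-capture |
|---|---|---|---|---|
| 2% | 16 | 11–14 | 51% | 38–47% |
| 5% | 40 | 28–36 | 87% | 73–83% |
| 8% | 64 | 45–58 | 97% | 89–95% |

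*If non-CV deaths were counted as CV events.* With 40 CV events and an assumed 4 to 12 such deaths, 4/44 = 9% to 12/52 = 23% of the event group would not be CV cases. The 0.5 SD difference would shrink to 0.5 × 40/44 = 0.45 SD or 0.5 × 40/52 = 0.38 SD. The plan does not say it will count deaths this way; this is only the cost of leaving the definition open.

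**The case against.** The strongest reply is that 8.7 lists data to be collected and is not a call script. Section 9.2(c) leaves follow-up procedures to a manual that is not among the documents, and that manual may ask more broadly. Verification in 8.7.2 is triggered by any reported event of interest, not only by the hospitalisation item, and its source documents are not limited to admission records. This stands in part: under-capture is likely if the listed items are followed, but it is not certain. A reader might infer that outpatient events can never reach adjudication, or that the call asks about nothing except admissions. The documents support neither, because the call also covers vital status and new chronic diagnoses.

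A reader might also infer that CV events will be pooled with non-CV deaths and cancers. No passage says so. Section 8.7.1 is headed as events of interest, the only list labelled cardiovascular (in 8.7) contains neither death nor cancer, and 8.7.2 obtains both the event type and the death certificate, so the categories can be separated. Mixing is a risk left open by the missing definition. All-cause death in the list does not itself cause under-capture.

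Finally, the power figures describe no planned test. Section 5.2 reports 20 to 25 thousand expressed genes, so a single-marker test at 5% is only a yardstick. That is correct, and the figures should be read for direction only.

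**Conclusion.** The mismatch holds: the cardiovascular call item is narrower than the events of interest, and verification does not close the gap. Non-admitted TIA or unstable angina and day-case coronary or peripheral angioplasty are the exposed categories. The undefined CV event, with no rule for cardiovascular death, is a lesser gap in detail that the same edit can close.

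The effect is mainly fewer captured events. Its size depends on the event rate, the outpatient share and the effect size, none of which the documents give. Under Illustration A the loss is 2 to 8 percentage points of power, and Illustration B gives larger losses where more events go unelicited. Severity is low: objective 2 is secondary and exploratory, and the primary coronary calcium objective rests on the baseline CT. The change is still worth making because it is cheap and missed events are hard to recover later.

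**What to change.** 1. Reword the cardiovascular item in 8.7 so that the caller asks for each 8.7.1 event, whether or not the patient was admitted. Carry the same wording into the manual of procedures.
2. In 8.7.2, have the adjudicators classify each death as cardiovascular or not, using the death certificate already among the source documents.
3. Define the CV event of objective 2 as cardiovascular death plus the cardiovascular entries of 8.7.1 (acute ischemic syndrome, heart failure, revascularisation, stroke or TIA). Report non-CV death and cancer separately.

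The cost is a revised call script, one adjudication field and slightly more source documents to request. Patient treatment, baseline procedures and the primary analysis do not change.

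### When a patient cannot be reached, section 8.7 seeks only vital status or a new number from the alternative contact, so non-fatal events may be missed in an outcome-dependent way

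*Combined protocol and SAP*

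**What the plan says.** Section 7.1 sets the aim of the follow-up: "a 5-year clinical (telephone) follow-up will be carried out to collect data on the incidence of fatal and non-fatal cardiovascular events". Section 8.7 gives the procedure: "Patients included in the study will be contacted annually by phone call to collect the following data". Three items follow: vital status, cardiovascular events, and new diagnoses of relevant chronic disease. The cardiovascular item is "New episodes of hospitalization due to acute ischemic syndrome, cerebrovascular event, heart failure or revascularization".

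For a patient who cannot be reached, the same section uses the alternative contact, whose telephone number is collected at baseline (section 8.2). The stated purpose is "in order to know their vital status or obtain a new contact number".

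Section 8.7.1 lists the events of interest. Among them are "Diagnosis of cerebrovascular accident", transient ischemic attack, new heart failure, cancer and death from any cause. Verification and adjudication in section 8.7.2 begin "When an event of interest is reported during study follow-up". Secondary objective 2 (section 6) compares blood transcriptomes between patients with and without a cardiovascular event during follow-up. The analysis plan (section 9.4) does not say how patients with incomplete follow-up are handled.

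**The concern.** The fallback asks for less than the call it replaces. Followed as written, it finds a death, because vital status is sought and death is an event of interest. It does not look for a stroke, an admission for heart failure or a new diagnosis.

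This differs from ordinary loss to follow-up because the reason for not answering may be the event itself. The more disabling a non-fatal event is, the likelier it is that a relative is the one reached. Three things follow:

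- Fatal and non-fatal events may be ascertained with different completeness.
- The non-fatal events that are captured may lean towards the milder ones.
- Secondary objective 2 has two groups and no category for unknown status, so a patient known only to be alive could be placed in the event-free group. The 5-year incidence could be understated for the same reason.

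**Working it through.** The plan gives no event rate, loss rate or follow-up calculation, so there is no figure of its own to reproduce. The sample size of 800 (section 9.3) is justified by algorithm training and not by follow-up events. The check therefore has two parts.

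**1. The two routes side by side**

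| Item | Patient reached | Only the alternative contact reached |
|---|---|---|
| Vital status | Asked | Sought |
| Cardiovascular events | Asked | Not listed |
| New diagnoses | Asked | Not listed |
| Death goes to 8.7.2 | Yes | Yes |
| Non-fatal event goes to 8.7.2 | Yes, once reported | If the contact volunteers it, or a later call recovers it |

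Sections 7.1, 8.7.2, 9.2 and 9.4 were read for anything that closes the gap. None describes a proxy interview, an active record search, registry linkage or an analysis rule for vital-status-only patients.

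**2. Scale, on assumed rates**

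Inputs: N = 800 (section 9.3); r = 5-year risk of a non-fatal event, assumed 2% to 6%; u = share of patients with an event who are never reached and whose event stays unrecorded, assumed 5% to 30%.

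Events E = N × r. Missed events M = E × u. Observed risk = (E − M) / N.

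| r | E | M at u = 5% | M at u = 10% | M at u = 30% |
|---|---|---|---|---|
| 2% | 16 | 0.8 | 1.6 | 4.8 |
| 4% | 32 | 1.6 | 3.2 | 9.6 |
| 6% | 48 | 2.4 | 4.8 | 14.4 |

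The range is 0.8 to 14.4, or about 1 to 14 events. At r = 4% the observed risk falls to (32 − 3.2)/800 = 3.6% with u = 10%, and to (32 − 9.6)/800 = 2.8% with u = 30%.

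For the event versus no-event comparison, assume a difference of 0.5 SD in a single expression measure, two-sided alpha 0.05, r = 4%, and missed events counted as event-free. Then n1 = E − M, n2 = N − E + M, the diluted difference is d = 0.5 × (1 − M/n2), and power = Φ(d / √(1/n1 + 1/n2) − 1.96).

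- Complete ascertainment: n1 = 32, n2 = 768, 0.5/0.1804 = 2.771, power Φ(0.811) = 79.1%.
- u = 10%: n1 = 28.8, n2 = 771.2, d = 0.4979, 0.4979/0.1898 = 2.624, power Φ(0.664) = 74.7%.
- u = 30%: n1 = 22.4, n2 = 777.6, d = 0.4938, 0.4938/0.2143 = 2.304, power Φ(0.344) = 63.5%.

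Dilution of the comparison group is slight: 3.2/771.2 = 0.4% and 9.6/777.6 = 1.2%. Nearly all the loss comes from having fewer events in the event group. The calculation also treats missed and captured events as alike in expression. If the missed ones are the more severe, a bias is added that these figures do not show.

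**The case against.** The strongest reply is that section 8.7 states a purpose and sets no prohibition. The word only does not appear. Section 8.7.2 does not say who must report an event, so a relative who explains that the patient has had a stroke has arguably reported one, and verification would follow. A new number may lead to a carer. The calls recur each year, so an admission missed at one call can be picked up at the next. The manual of procedures promised in section 9.2 will describe follow-up and may hold the call script. A narrow proxy role can also be defended on privacy grounds. Finally, the affected objective is exploratory.

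Much of this stands, and it rules out stronger readings that a reader might infer:

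- **That proxy reports are barred, or that such events are certain to be lost.** The text supports neither. Events may be missed; a volunteered report, a new number or a later call may recover them.
- **That these patients are recorded as event-free.** No section codes them so. The documents have no rule, which leaves that coding possible.
- **That the diagnostic accuracy result is undermined.** It rests on the baseline CT and does not use follow-up events.

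The objection does not remove the gap. Capture of a non-fatal event should not depend on what a relative happens to mention. The manual is still to be written and would be expected to follow the protocol's sentence, which names two purposes and omits events.

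**Conclusion.** The point holds in a limited form. Section 8.7 gives the fallback contact a narrower task than the patient call, so non-fatal cardiovascular events and new diagnoses are not actively sought when a patient cannot be reached. Because stroke or heart failure can cause the unreachability, the resulting loss may depend on the outcome.

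The effect is confined to exploratory secondary objective 2 and the 5-year incidence. Its size cannot be derived from the documents. The figure of about 1 to 14 missed events rests wholly on the assumed 2% to 6% risk and 5% to 30% never reached. The fall in power from 79.1% to between 74.7% and 63.5% rests further on an assumed 4% risk, a 0.5 SD difference, and missed events being counted as event-free. The upper end needs 30% of patients with an event never to be reached, for which the documents offer no support either way. The change is worth making because events are few under these assumptions, the call is already being made, and unrecorded events are hard to recover years later.

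**What to change.** Amend the sentence in section 8.7 so that, when the patient cannot be reached or cannot answer, the alternative contact is asked the same items as the patient: vital status, cardiovascular events and new diagnoses. Record the source as proxy, and send any event reported this way to the verification step in 8.7.2. First check that the consent form, which is not in the text available here, covers asking a third party and obtaining source documents; add a line if it does not.

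Add a rule to section 9.4: a contact that yields vital status alone is recorded as event status unknown since the last full contact, not as no event. This does not remove outcome-dependent loss, but it makes the loss visible and prevents silent misclassification. The number of such patients should be reported beside the results of secondary objective 2 and the 5-year incidence.

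The cost is one amended sentence, one source field on the follow-up form, one analysis rule and possibly a consent line. The downsides are slightly longer proxy calls, less certain proxy reports (which 8.7.2 can check) and a privacy point that consent must cover.
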